**Limb Reduction/Addition Defects (LIMB)**  
Absence of complete upper limb  
Absence of upper arm and forearm (hand present)  
Absence of upper arm  
Absence of forearm  
Absence of hand/fingers  
Preaxial reduction defect—arm/hand  
Postaxial reduction defect—arm/hand  
Ectrodactyly hand  
Transverse reduction defect of upper limb NOS  
Longitudinal reduction defect of upper limb NOS  
Other specified reduction defect of the arm  
Unspecified reduction defect of the arm  
Absence of complete lower limb  
Absence of thigh and calf (foot present)  
Absence of thigh  
Absence of calf  
Absence of foot/toes  
Preaxial reduction defect—leg/foot  
Postaxial reduction defect—leg/foot  
Ectrodactyly foot  
Transverse reduction defect of lower limb NOS  
Longitudinal reduction defect of lower limb NOS  
Other specified reduction defect of the leg  
Unspecified reduction defect of the leg  
Specified or unspecified reduction defect of unspecified limb  
Absent digits NOS

Polydactyly—postaxial hand  
Skin tags in blacks\*  
Polydactyly—preaxial hand  
Polydactyly—postaxial foot  
Skin tags in blacks\*  
Polydactyly—preaxial foot  
Polydactyly NOS—hand  
Polydactyly NOS—foot  
Other and unspecified polydactyly  
Other limb addition anomaly  
**Other Musculoskeletal Defects (MS-O)**  
Microcephaly  
Macrocephaly (without hydrocephalus)  
Abnormal shape of head—no craniosynostosis  
Dolichocephaly excluded < 36 weeks\*  
Scaphocephaly excluded < 36 weeks\*  
Sagittal craniosynostosis  
Coronal craniosynostosis  
Metopic craniosynostosis  
Lambdoidal craniosynostosis  
Other and unspecified craniosynostosis  
Acrocephalosyndactyly of any type  
Oculoauriculovertebral spectrum/Hemifacial microsomia  
Other specified craniofacial malformation syndrome  
Other specified anomaly of skull and/or face bone  
Large/small fontanelle\*  
Flat occiput\*  
Prominent occiput\*  
Unspecified anomaly of skull and/or face bones  
Pectus carinatum  
Pectus excavatum  
Absent sternum  
Other and unspecified anomaly of sternum  
Anomaly of chest wall  
Absent ribs  
Extra ribs (including cervical)  
Cervical rib\*  
Fused or bifid ribs  
Other and unspecified anomaly of ribs  
Spina bifida occulta/sacral dimple  
Scoliosis/kyphoscoliosis without vertebral anomaly  
Anomaly of cervical vertebra  
Anomaly of thoracic vertebra  
Anomaly of lumbar vertebra  
Anomaly of sacrum/coccyx  
Other and unspecified vertebral anomaly  
Syndactyly—fingers  
Syndactyly—toes  
Webbing of second and third toes\*  
Unspecified syndactyly  
Anomaly of fingers  
Clinodactyly of fifth finger\*  
Long fingers\*  
Anomaly of hand, including palmar creases  
Club hand  
Anomaly of wrist  
Anomaly of forearm  
Anomaly of elbow, including dislocation  
Anomaly of upper arm/humerus  
Anomaly of shoulder, including clavicle

Erb palsy  
 Hypoplasia of arm  
 Poland Anomaly/Absent chest muscle  
 Other specified anomaly of upper extremity  
 Unspecified anomaly of upper extremity  
 Anomaly of toes  
 Overlapping toes\*  
 Anomaly of foot (excluding club foot)  
 Rocker-bottom foot\*  
 Anomaly of ankle  
 Anomaly of calf  
 Excluded: Tibial torsion with clubfoot  
 Anomaly of knee/patella, including dislocation  
 Anomaly of thigh/femur  
 Anomaly of hip, excluding hip dysplasia  
 Hip dysplasia/dislocation  
 Hypoplasia of leg  
 Other specified anomaly of lower extremity (excluding club foot)  
 Unspecified anomaly of lower extremity  
 Varus (inward) anomaly of foot  
 Metatarsus varus/adductus\*  
 Valgus (outward) anomaly of foot  
 Other and unspecified club foot  
 Other specified anomaly of unspecified limb  
 Unspecified anomaly of unspecified limb  
 Arthrogyposis  
 Chondrodystrophy/'Dwarfism'  
 Osteodystrophy  
 Other specified skeletal dysplasia  
 Unspecified skeletal dysplasia  
 Diaphragmatic hernia  
 Other anomaly of diaphragm  
 Umbilical Hernia\*  
 Inguinal Hernia  
 Never code < 36 weeks ≥ 36 weeks, always code in female, conditional in male  
 Omphalocele  
 Gastroschisis  
 Absence of abdominal musculature/Prune Belly  
 Other specified anomaly of anterior abdominal wall  
 Includes Limb-Body Wall complex  
 Unspecified anomaly of anterior abdominal wall  
 Other and unspecified anomaly of muscle  
 Other and unspecified anomaly of tendon  
 Other and unspecified anomaly of bone  
 Other and unspecified anomaly of cartilage  
 Other and unspecified anomaly of connective tissue  
 Other and unspecified anomaly of musculoskeletal system  
 Sacral/pilonidal dimple\*  
 Erb palsy\*  
**Skin and Skin Derivatives (SKIN)**  
 Absence of skin  
 Ichthyosis  
 Epidermolysis Bullosa  
 Ectodermal dysplasia  
 Hyperpigmentation  
 Excluded: Mongolian spots  
 Port wine stain\*

Nevus flammeus\*  
 Cafe-au-lait spots\*  
 Hypopigmentation  
 Skin tags (not face/neck)  
 Birthmark NOS\*  
 Cutis aplasia (scalp)  
 Benign tumor of skin  
 Sebaceous cyst  
 Hairy nevus  
 Other specified anomaly of skin  
 Transvers plamar creases\*  
 Anal tags\*  
 Skin cysts\*  
 Persistent lanugo\*  
 Unspecified anomaly of skin  
 Anomaly of hair  
 Anomaly of nails  
 Anomaly of breast  
 Excluded: Inverted nipples  
 Small nipple\*  
 Accessory/ectopic/supernumerary nipple\*  
 Widely spaced nipples\*  
 Other specified anomaly of skin derivative  
 Unspecified anomaly of skin derivative  
**Chromosome Anomaly (CHROM)**  
 Specific list would include any abnormal chromosome complement and will be clearly defined in affected individuals. For example:  
 Trisomy 13  
 Trisomy 21  
 Turner Syndrome NOS  
 Unspecified mosaicism  
 Unspecified translocation  
 Unspecified additional chromosome(s)  
 Unspecified deletion of chromosome  
 Unspecified duplication of chromosome  
 Unspecified chromosome anomaly  
**Other Organs and Organ Systems (OTHER)**  
 Conjoined twins  
 Amniotic band/Amnion rupture sequence\*  
 Absence/hypoplasia of spleen  
 Accessory spleen  
 Ectopic spleen  
 Other and unspecified anomaly of spleen  
 Hyperplasia of spleen/splenomegaly\*  
 Absence/hypoplasia of adrenal gland  
 Accessory adrenal gland  
 Ectopic adrenal gland  
 Other and unspecified anomaly of adrenal gland  
 Anomaly of pituitary gland  
 Anomaly of thyroid gland  
 Hypothyroidism\*  
 Anomaly of parathyroid gland  
 Hypoparathyroidism\*  
 Anomaly of thymus  
 Thymic hypertrophy\*  
 Other and unspecified anomaly of endocrine gland  
 Hypoglycemia\*  
 Heterotaxy syndrome  
 Ambiguous genitalia in infant of unknown gender  
 Hermaphroditism

---

Male pseudohermaphroditism  
Female pseudohermaphroditism  
Other and unspecified anomaly of sex assignment  
Congenital anomaly NOS  
Anomaly of placenta  
Anomaly of umbilical cord (other than single umbilical artery)  
Umbilical cord atrophy\*  
Lipoma  
Teratoma  
Ascites/Hydrops\*

**Specified Syndromes/Sequences/Associations (SYND)**

This list would be exhaustive and could include anything that is a recognized, named syndrome. Occurrence of any one syndrome will probably be rare.

Congenital Adrenal Hyperplasia  
Fetal Alcohol Syndrome  
Neuroblastoma  
Potter Sequence  
Roberts Syndrome  
Twin-Twin Transfusion  
Water Association  
Velocardiofacial Syndrome—possible  
Zellweger Syndrome  
Congenital syphilis\*  
Benign neoplasms\*  
Phenylketonuria and other inborn errors of metabolism  
not usually associated with birth defects\*

---

\*These items are only included under certain circumstances. Unless otherwise specified for the item, the item is only included if there is another ascertainable defect.

Items marked as 'excluded' are never considered defects.

TLF	Tables, Listings, and Figures
WHO-DD	World Health Organization Drug Dictionary

3 Modification History

Unique Identifier for Version	Date of IAP Version	Author	Changes from the Previous Version
NA			

4 Purpose of the Integrated Analysis Plan

The purpose of this IAP (integrated analysis plan) is to document technical and detailed statistical specifications for the final analysis of data collected for protocol EMR700568-012 called PREMIERE. Results of the analyses described in this IAP will be included in the Clinical Study Report (CSR). Additionally, the planned analyses identified in this IAP will be included in regulatory submissions or future manuscripts. Any post-hoc, or unplanned analyses performed to provide results for inclusion in the CSR but not identified in this prospective IAP will be clearly identified in the CSR.

The IAP is based upon section 9 (Data Analysis and Statistics) of the study protocol and protocol amendments and is prepared in compliance with International Conference on Harmonization (ICH) E9 and Guidelines for Good Pharmacoepidemiology Practices (GPP). It describes analyses planned in the protocol and protocol amendments.

5 Objectives and Endpoints

Objectives	Endpoints (Outcome Measures)	Endpoints (Outcome Measures) Timeframe	IAP section
Primary			

 To quantify and characterize the risk (cumulative incidence) of serious adverse drug reaction (SADR), including malignancies and serious infections To assess time to resolution of lymphopenia among registry participants with persistent lymphopenia To quantify and characterize the risk (cumulative incidence) of AE in the 'Blood and Lymphatic System Disorders' and 'Neoplasms Benign, Malignant, and Unspecified' System Organ Classes (SOCs) 	
 Cumulative incidence of SADR, including malignancies and serious infections Time to resolution of lymphopenia, among registry participants with persistent lymphopenia Cumulative incidence of all AEs in the "Blood and Lymphatic System Disorders" System Organ Class (SOC) and in the "Neoplasms Benign, Malignant, and Unspecified" SOC 	
 AE crude incidence from Registry Day 1 to End of registry Time to resolution of lymphopenia, for participants with ongoing lymphopenia at the end of clinical trial AE crude incidence from Registry Day 1 to End of registry 	
 Section 15.1.1 Section 15.1.4 Section 15.1.2 & 15.1.3
Secondary			

 To assess pregnancy outcomes, including congenital malformations or other important health conditions in the offspring born to women exposed to oral cladribine 	
 Pregnancy outcomes, including congenital malformations, spontaneous abortion, elective abortion, stillbirth, ectopic pregnancy, molar pregnancy, and other important health conditions in the offspring 	
 Number of patients with pregnancies from Registry Day 1 to End of registry and descriptive statistics of pregnancy outcomes 	
 Section 15.2

6 Overview of Planned Analyses

Summary of PREMIERE registry

The PREMIERE study is an ongoing prospective observational long-term safety registry of patients who have participated in at least one of the 5 cladribine clinical trials (namely CLARITY [25643], CLARITY EXT [27820], ONWARD [26593], ORACLE [28821] and the pantoprazole drug-drug interaction [DDI] phase I study [27967]). These 5 studies are referred throughout this document under the general term "clinical trials".

The original objectives of the PREMIERE registry were to monitor long-term safety events in a clinical trial population to produce long-term safety data in order to better characterize the potential safety risks of oral cladribine, and to build an evidence-based risk minimization strategy. The study was amended with simplification and including restriction to serious adverse drug reactions (SADR), selected AEs (all AEs in the 'Blood and Lymphatic System Disorders' and 'Neoplasms Benign, Malignant, and Unspecified' SOCs) and reduction of frequency of assessments. The duration of follow-up in the registry is up to the end of the registry or 8 years after the subject's first enrolment into a cladribine clinical trial, whichever occurs first. Last patient last visit for the final analysis was on October 25th, 2018.

[figure not shown]

Figure 1 PREMIERE Registry Overview Diagram

6.1 Intermediate Analyses

Two intermediate safety synoptic reports have been performed while the study was ongoing (REF. CSR items #1 and #2). The data cut-off for the first analysis was 20 February 2015 and the cut-off for the second analysis was 15 May 2017.

6.2 Final Analysis

All final, planned analyses identified in the Clinical Study Protocol and in this IAP will be performed only after the last participant has completed the study (following protocol definition) with all study data in-house, all data queries resolved as much as possible, and the database locked.

7 Changes to the Planned Analyses in the Clinical Study Protocol

As usual, Statistical Analysis Plans are more detailed than relevant sections of the Study Protocols; such additions and refinements are therefore not mentioned in this section. Instead, only true deviations from statements in the study protocol are listed together with a brief rationale.

Table 1 Changes from the planned analyses in the clinical study protocol

Protocol Section: Item	Protocol definition	Changes implemented in the SAP
Section 5.6: Study Cohort	There will be no control/comparison group	"Never exposed to Cladribine" group will be considered as reference for a long-term non-treated population.
Section 9.2.2: Treatment/Analysis periods	
The most relevant analysis period will be the cumulative analysis period, which starts from the date of first dose of clinical trial medication to the end of the registry follow-up. In addition of the cumulative period, three treatment periods are identified:
 
a) the initial treatment period, from the date of first dose of clinical trial medication to end of the clinical trial participation; b) the extension treatment period (when subjects elects to enroll in a cladribine extension trial) from the date of first dose of cladribine to the end of extension trial participation, c) and the registry study period (where subjects do not receive any experimentally assigned treatment) from the date of enrollment into the registry to the end of registry participation.
 
The primary analysis will correspond to the cumulative analysis period, which starts from the date of first dose of clinical trial medication to the end of registry follow-up.
	
The primary analysis will NOT start from the date of first dose of clinical trial medication to the end of registry follow-up. Reporting for the clinical trial period has been presented in each individual study CSR. In the Integrated Summary of Safety (ISS) for the proposed indication of Cladribine in the treatment of adult patients with relapsing forms of Multiple Sclerosis (RMS), long-term data available at the cut-off date of 15 May 2017 has already been presented exhaustively, including all subjects – those enrolled and those not enrolled in PREMIERE.
 
In order to focus on the long-term safety events that were collected during the registry follow-up, the analysis period for the safety analysis population will be the time from the end of clinical trial + 1 day to the last date in PREMIERE registry.
 
In addition, two analysis periods for the lymphocyte analysis population will be defined:
 
 • The time from first dose of cladribine/placebo* in clinical trials to the last Absolute Lymphocyte Count (ALC) date with a value available in PREMIERE registry

		
 • The time from first ALC date with value in PREMIERE registry to the last ALC date with a value available in PREMIERE registry * A subject who switches treatment from placebo to cladribine in subsequent studies/periods will be considered from first dose of cladribine and the placebo period will not be considered.
Section 9.2.2 Treatment/Analysis periods	Demographic characteristics (e.g., age, sex) at baseline of the registry will be described using descriptive statistics for continuous variables or proportions for categorical variables at entry into the registry. Summaries will be provided by region/country.	Demographic characteristics will not be summarized by region/country. Instead, based on the understanding of the protocol, summary statistics for the number of subjects by country will be provided.
Section 9.2.1 General Considerations	Time to resolution of persistent lymphopenia will be estimated using the life table methodology.	
The time to resolution of lymphopenia (duration of lymphopenia episode) has already been presented in the ISS using the product-limit method of Kaplan and Meier. This analysis will not be repeated.
 
The time to resolution of lymphopenia for participants with ongoing lymphopenia at end of clinical trial will be analyzed using descriptive statistics.

Section 9.2.1 General Considerations	The main analysis will be to estimate cumulative incidence rates using life-table methodology.	
The main analysis of adverse events will be done on the period from the end of clinical trial + 1 day to the last date in PREMIERE registry. The life-table methodology will not be used. Rather, the crude incidence will be presented with the corresponding 95% confidence interval.
 
The time to first event from the first dose of cladribine has already been presented in the ISS following the Kaplan-Meier methodology for AESI infections and malignancies. Therefore, it will not be repeated here.

Section 10.2 Subject information and informed consent	Subjects who refuse to enroll in the registry will be asked to sign consent (see CRF: Data Release Participant only) for use of their clinical trial data to compare registry non-participants with registry participants in terms of demographics, cancer risk factors and severity of MS.	Comparison of registry participant's vs non-registry participants will not be performed due to very strong sample size imbalance between the 2 groups. Indeed as the registry target population was of 2175 subjects, 1161 patients enrolled as full participants and 22 refused and signed the data release consent form only.
---	---	---

8 Protocol Deviations and Analysis Populations

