## 5.6 Study Cohort

The cohort of cladribine-treated subjects will consist of all subjects who have consented to participate and who were treated with cladribine during the clinical trial period of the identified clinical trials or cladribine extension studies in MS.

There will be no control/comparison group. Subjects who were on placebo during a clinical trial but who switched to cladribine in the extension study will contribute person-time to the cohort of cladribine-treated subjects from the moment they initiate cladribine. Person-time prior to cladribine initiation in subjects originally randomized to placebo, will not be used in the calculation of study endpoints incidences.

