## 9.2.2                      Treatment/Analysis Period

The most relevant analysis period will be the cumulative analysis period, which starts from the date of first dose of clinical trial medication to the end of the registry follow-up. In addition, three treatment periods are identified: a) the initial treatment period, from the date of first dose of clinical trial medication to end of the clinical trial participation; b) the extension treatment period (when subjects elects to enroll in a cladribine extension trial) from the date of first dose of cladribine to the end of extension trial participation, c) and the registry study period (where subjects do not receive any experimentally assigned treatment) from the date of enrollment into the registry to the end of registry participation.

The primary analysis will correspond to the cumulative analysis period, which starts from the date of first dose of clinical trial medication to the end of registry follow-up.

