9.1 Treatment groups

Analyses will be performed on the "as treated principle", where patients are allocated to the treatment group that they actually received in the clinical trial studies (which may be different from the study treatment to which they were randomized to).

Patients are assigned to the following treatment groups according to their actual treatment in one of the studies CLARITY alone, ONWARD, CLARITY/CLARITY EXTENSION, ORACLE MS, Pantoprazole DDI.

- **Never exposed to cladribine:** if a subject has taken only placebo (or placebo +IFN-β) in studies, then her/his data becomes part of the "Never exposed to cladribine" treatment group. A subject who switches treatment from placebo to cladribine in subsequent studies/periods **will not** be considered in this group.
- **Exposed to cladribine:** patients with at least one dose of cladribine. Subjects who were on placebo during the clinical trial and switched to cladribine in the extension study will contribute to the treatment group "Exposed to cladribine" from the moment they initiate cladribine.

An example of the header for table outputs is presented below.

Table 2 Table header example

	Never exposed to Cladribine (N=XXXX)	Exposed to Cladribine (N=XXXX)	Total (N=XXXX)
Safety Analysis Population	xxx (100.0)	xxx (100.0)	xxx (100.0)

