- 95% Confidence Interval (CI) for the crude incidence within group for patients with at least one AE. The 95% Confidence Interval of the AE will be computed using the exact Clopper-Pearson confidence interval formula for binomial proportions (REF. Clopper item #3).

Statistics description

The following statistics per treatment group and total will be presented:

- Summary: Patient-years will be provided in the summary table. In addition, number of unique event, number of patients with at least one AE, crude incidence (%), 95% CI of the crude incidence. All these statistics will be repeated for AE leading to death and serious AE.

Note: SADR is a serious AE by definition. Therefore, only SADR and SADR leading to death will be presented.

- By SOC/ HLGT/ HLT/PT: Number of patients with the AE and crude incidence (%) will be presented by system organ class (SOC), High Level Group Term (HLGT), High Level Term (HLT), and preferred term (PT).

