15.5 Adverse Event of Special Interest

The term Adverse Events of Special Interest represents a broader than usual category of events for which specific attention will be paid during the review of the results.

The following statistics will be presented:

- Summary: Patient-year, number of unique event, number of subjects with at least one event, crude incidence and 95% CI per treatment group. All these statistics will be repeated for AE leading to death and serious AE.

In addition, summary table will be repeated by

- CLARITY only
 - CLARITY/CLARITY EXTENSION
 - ORACLE MS
 - ONWARD
- By PT: Number of patients with the AE and crude incidence (%) per treatment group and total will be presented.

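### The incidence primary endpoints show pooled exposed and never-exposed groups side by side, without the by-trial repeat that the SAP gives its AESI tables

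*SAP*

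**What the plan says.** Protocol 5.6 is explicit: "There will be no control/comparison group". SAP section 7, Table 1 lists a deviation from this. The never-exposed "group will be considered as reference for a long-term non-treated population".

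SAP 9.1 defines the groups. A subject is never exposed "if a subject has taken only placebo (or placebo +IFN-β) in studies". The rule for switchers has two parts. "A subject who switches treatment from placebo to cladribine in subsequent studies/periods" is kept out of the never-exposed group, and "Subjects who were on placebo during the clinical trial and switched to cladribine in the extension study will contribute to the treatment group" of the exposed from their first cladribine dose. Protocol 9.2.2 describes entry to the extension as a choice: "when subjects elects to enroll in a cladribine extension trial".

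The Safety Analysis Population (SAP 8.2) pools registry participants from CLARITY, CLARITY EXT, ORACLE MS and ONWARD. SAP 15.1.1 introduces its displays with "The following statistics per treatment group and total will be presented". They give patient-years, event counts, crude incidence n/N and a within-group Clopper-Pearson interval. Sections 15.1.2 and 15.1.3 reuse that layout for the Blood and Lymphatic SOC and the Neoplasms SOC. None of the three asks for a repeat by trial.

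Elsewhere the SAP does ask for one. Section 15.5 on AESIs says "In addition, summary table will be repeated by" and lists the four trial groups, and section 10.1 does the same for disposition. Section 11.1 also tabulates previous clinical trial by treatment group.

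**The concern.** Once a column is called a reference, readers will compare it with its neighbour. SAP 9.14 plans no inference but bases interpretation on point estimates and 95% intervals, and those are what stand side by side.

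The two columns do not draw on the four trials in the same proportions. Moving placebo switchers to the exposed group leaves CLARITY/CLARITY EXTENSION with few or no never-exposed subjects. The other three strata keep theirs, and the never-exposed subjects left in CLARITY are those who did not switch. If event risk or time at risk differs between trials, the crude columns differ with no drug effect, or agree when there is one.

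The documents supply a route for unequal time at risk. The analysis period starts the day after the last trial ends (SAP 9.2), while follow-up stops at registry end or 8 years after first trial entry (SAP section 6). More time in trials therefore leaves less time after them. The crude percentage takes no account of this, although patient-years are printed.

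The word non-treated is also inaccurate. The group includes placebo plus IFN-β subjects, and either group may take MS disease-modifying drugs during the registry (SAP 12.2.1).

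**Working it through.** The plan states no sample size, event count or contrast for this comparison, so there is no figure to reproduce. The questions are whether the by-trial mix alone can move the crude ratio, and by how much.

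**From the documents:** the grouping rule (SAP 9.1), the pooled population (SAP 8.2), the crude measure (SAP 15.1.1), and 1161 full participants out of a target of 2175 (SAP Table 1), which is 1161/2175 = 53.4%.

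**Not in the documents, so assumed:** exposed and never-exposed counts by trial, event risks by trial, and post-trial time by trial.

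**1. Different risk in the extension stratum, no drug effect.** Let w be the share of the exposed who come from the extension stratum, taken as all exposed. Let r be the risk in the other trials and k·r the risk in the extension stratum. Then

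- crude risk, exposed = w·k·r + (1 − w)·r
- crude risk, never exposed = r
- crude risk ratio = w·k + (1 − w)

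| w | k = 0.5 | k = 1 | k = 2 |
|---|---|---|---|
| 0.3 | 0.85 | 1.00 | 1.30 |
| 0.5 | 0.75 | 1.00 | 1.50 |
| 0.7 | 0.65 | 1.00 | 1.70 |

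**2. Four-stratum example, no drug effect.** Assumed exposed/never-exposed counts are CLARITY only 220/130, CLARITY/EXTENSION 450/0, ORACLE MS 160/80 and ONWARD 80/41. That is 910/251, or 1161 in all. The 1161 is used only as a convenient total, because the SAP figure is not restricted to the Safety Analysis Population. Base risk is 3%.

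- Extension risk doubled: exposed (460 × 0.03 + 450 × 0.06)/910 = 40.8/910 = 4.48%; never exposed 3.0%; ratio 1.49.
- Extension risk halved: exposed (13.8 + 6.75)/910 = 2.26%; never exposed 3.0%; ratio 0.75.
- Extension doubled and ORACLE MS halved: exposed 38.4/910 = 4.22%; never exposed 6.33/251 = 2.52%; ratio 1.67.
- All trials at one risk: ratio 1.00.

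A Mantel-Haenszel ratio stratified by trial is 1.00 in every case. In the first case, with events rounded to whole numbers, the Clopper-Pearson intervals are 3.3% to 6.1% (exposed) and 1.4% to 6.2% (never exposed). They reflect sampling error only and say nothing about the mix.

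**3. Follow-up alone, equal hazards.** Assume 4 post-trial years for extension subjects, 6 for the others, and a hazard of 1% per year. The risks are 1 − exp(−0.04) = 3.92% and 1 − exp(−0.06) = 5.82%, so k = 0.673. The crude ratio is 0.90, 0.84 and 0.77 for w = 0.3, 0.5 and 0.7. The ratio of events per patient-year stays between 1.00 and 1.01. This distortion runs towards hiding an excess.

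**4. What the existing by-trial tables cover.** The AESI repeats cover infections and malignancies, including serious and fatal events. They do not cover overall SADR, the Blood and Lymphatic SOC, or non-malignant neoplasms. Time to resolution of lymphopenia does not use this crude comparison and is not affected.

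**The case against.** The strongest reply is that the SAP plans no comparison at all. It contains no difference, ratio or test, and its intervals are within group. The imbalance will also be visible, because previous trial is tabulated by treatment group and disposition is repeated by trial with patient-years. Infections and malignancies, the event types named in the first primary endpoint, already have by-trial AESI summaries. The output column header already reads never exposed to cladribine, so non-treated is a wording slip in one table. Most of this stands, and it narrows the gap. It does not close it: seeing that the mix differs does not tell a reader how far it moved the incidence of the endpoints left out.

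Two stronger readings are tempting.

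- A reader might infer that the pooled tables will show a false excess on cladribine. The documents do not support a direction. The range in the working straddles 1, and unequal follow-up alone pushes the ratio below 1.
- A reader might infer that stratifying by trial recovers the randomised comparison. It does not. Extension entry was elective, switchers moved group, and 53.4% of the target population joined the registry as full participants. A CLARITY-only contrast remains selected on both sides.

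A stratified exposed-minus-never difference would also be ill-posed for SADR. SAP 15.1.1 requires a probable or possible relationship to cladribine, and the never-exposed took none. The contrast would largely measure attribution.

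**Conclusion.** The concern holds as a presentational and confounding gap in three primary-endpoint displays. The SAP names a reference group, pools trials whose exposed/never mix must differ under its own grouping rule, and omits for these endpoints the by-trial repeat it uses elsewhere. The gap is overall SADR, the Blood and Lymphatic SOC and non-malignant neoplasms.

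The size cannot be fixed from the documents. The 0.65 to 1.70 range rests on three assumptions: no drug effect, an all-exposed extension stratum making up 30% to 70% of the exposed, and a common risk in the other trials with the extension at 0.5 to 2 times that risk. If all trials share one risk and similar follow-up, there is no distortion. This is a cheap improvement to a descriptive plan and does not invalidate it.

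**What to change.** 1. Repeat the summary tables of SAP 15.1.1 to 15.1.3 by previous clinical trial, using the four groups and layout of 15.5. The 15.1.1 summary already carries patient-years, so these would then appear by trial and group too.
2. If the report sets the two groups against each other for the Blood and Lymphatic or Neoplasms SOC endpoints, add a trial-stratified difference with a 95% CI, for estimation only, restricted to trials that contain both groups. SAP reference 6, on comparing two rates, is already listed. State beside it that the restriction drops extension subjects and that elective switching and registry consent still leave selection.
3. Do not compute this difference for SADR.
4. In SAP Table 1, replace the non-treated wording with *never exposed to cladribine in the trials; other MS treatment allowed*.

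The cost is SAP wording and repeats of existing table shells, with no new data. The downside is more tables, sparse within-trial cells and wider intervals.
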